38 mos. from study start; all 825 subjects enrolled and followed up for at least 17 months	PFS mono/combo vs. SOC in subjects with PD-L1 CPS 20 (H1/H4)	~237	Z statistic p-value (one-sided) Approx. observed HR	2.9775 0.0015 0.6792
	PFS mono/combo vs. SOC in subjects with PD-L1 CPS 1 (H2/H5)	~378	Z statistic p-value (one-sided) Approx. observed HR	2.9755 0.0015 0.7363
	PFS mono vs. SOC in all subjects (H3)	~474	Z statistic p-value (one-sided) Approx. observed HR	2.9755 0.0015 0.7606
	PFS combo vs. SOC in all subjects (H6)	~474	Z statistic p-value (one-sided) Approx. observed HR	3.5924 0.0002 0.7188

[†] Efficacy decision rules for PFS presented in table do not account for any alpha shifting from other hypotheses as a result of a successful analysis. P-values based on spending functions determine significance of tests; hazard ratios corresponding to significance are approximate.

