2.0 TRIAL DESIGN

2.1 Trial Design

This is a randomized, active-controlled, multi-site, open-label trial of pembrolizumab, or pembrolizumab plus platinum plus 5-FU chemotherapies versus platinum plus 5-FU plus cetuximab in subjects with advanced head and neck cancer to be conducted in conformance with Good Clinical Practices (GCP). Approximately 825 subjects with first line recurrent or metastatic (R/M) head and neck cancer will be enrolled for examination of the efficacy and safety of pembrolizumab versus pembrolizumab plus chemotherapy versus standard of care with cetuximab and chemotherapy. Subjects will be randomized 1:1:1 between the 3 arms of the trial.

The study will be stratified. Stratification factors are described in Section 5.4.

Specific procedures to be performed during the trial, as well as their prescribed times and associated visit windows, are outlined in the Trial Flow Chart - Section 6.0. Details of each procedure are provided in Section 7.0 – Trial Procedures.

[figure not shown]
This trial will use a group-sequential design based on pre-specified criteria, using an independent, external DMC to monitor safety and efficacy. There will be 2 interim PFS/OS analyses, 1 final OS analysis, 1 planned interim safety analysis, and quarterly safety monitoring. The interim safety analysis will be conducted when 10 subjects in the pembrolizumab plus chemotherapy arm have completed 2 cycles of treatment. The interim PFS/OS analyses are time-driven. More details are given in Section 8.2.9.

Results of the interim analyses will be reviewed by the DMC, which will make recommendations to the Sponsor to continue, modify, or end the trial according to the plan described briefly in Section 2.2 - Trial Diagram and in detail in Section 8.0 - Statistical Analysis Plan.

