8.2.9.2 Efficacy Interim Analyses

Two interim analyses are currently planned. Results will be reviewed by an external DMC. Further details of interim analyses are provided below and will be incorporated into the DMC charter.

For each PFS and each OS hypothesis, a Hwang-Shih-DeCani alpha-spending function with gamma parameter (-4) is constructed to implement group-sequential efficacy boundaries to control the type I error. The same spending function used for OS superiority hypotheses is also implemented to calculate boundaries for the noninferiority hypotheses. [Table 23](#) provides more details on the timing, number of events and decision guidance for each analysis. The actual boundaries and the alpha level will be determined from the overall alpha level after alpha shifting as a result of a successful analysis and the actual number of events observed at the time of the interim analysis using the corresponding alpha-spending function.

In the event that superiority is declared for one or more PFS hypotheses at interim analysis 1, the study will continue to follow subjects for OS unless substantial treatment effect is demonstrated for all OS hypotheses at the significance level determined from the alpha-spending function as specified above.

Interim Analysis 1: interim PFS/OS analyses

The interim analysis will take place when all subjects have been followed up for at least 9 months.

Assuming 21 months enrollment period for 825 all subjects, interim analysis 1 is projected to occur 30 months after study start. The primary objective of the analyses is to demonstrate PFS superiority of pembrolizumab (monotherapy or in combination with chemotherapy).

At the time of interim analysis 1, the expected numbers of PFS events observed for the PFS hypotheses are specified below. If the actual number of events for a PFS hypothesis is different, the spending function boundaries will be adjusted accordingly for the actual number of events for that PFS hypothesis.

- ~211 PFS events between one experimental treatment and standard treatment in subjects with PD-L1 CPS 20 (H1 and H4)
- ~337 PFS events between one experimental treatment and standard treatment in subjects with PD-L1 CPS 1 (H2 and H5)
- ~423 PFS events between one experimental arm and standard treatment in all subjects (H3 and H6)

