- ~278 deaths between one experimental arm and standard treatment in subjects with PD-L1 CPS 1 (H8 and H12)

- ~352 deaths between one experimental arm and standard treatment in all subjects (H9, H10, H13 and H14)

The hazard ratio at bound, significance level and Z statistics of OS hypotheses provided in [Table 23](#) are based on a nominal overall one-sided alpha level of 0.7% each to pembrolizumab monotherapy vs. standard treatment, and pembrolizumab in combination with chemotherapy vs. standard treatment, though the overall alpha levels for the OS hypotheses may be more than 0.7% due to alpha shifting as a result of success in other hypotheses. The actual alpha level for an OS hypothesis will be recalculated if the overall alpha level is not the same as the specified nominal alpha level given the multiplicity strategy or the expected number of deaths is not observed.

Interim Analysis 2: interim OS analyses and final PFS analyses

The interim analysis will take place when all subjects have been followed up for at least 17 months.

Assuming 21 months enrollment period for 825 all subjects, interim analysis 2 is projected to occur 38 months after study start. The primary objective of the analyses is to demonstrate OS superiority of pembrolizumab (monotherapy or in combination with chemotherapy).

The expected numbers of events for the OS hypotheses are:

- ~205 deaths between one experimental arm and standard treatment in subjects with PD-L1 CPS 20 (H7, H11);
- ~332 deaths between one experimental arm and standard treatment in subjects with PD-L1 CPS 1 (H8, H12);
- ~421 deaths between one experimental arm and standard treatment in all subjects (H9, H10, H13 and H14).

However, if the expected number of events for an OS hypothesis is not observed, then the spending function boundaries will be adjusted accordingly for the smaller number of events for that OS hypothesis.

For the hypotheses of OS superiority of one experimental treatment in subjects with PD-L1 CPS 20 (H7 and H11), an alpha level of 0.7% is allocated to each test. The boundary to demonstrate OS superiority of one experimental treatment over standard treatment in PD-L1 CPS 20 corresponds to a one-sided p-value of 0.0041, which corresponds to an approximate observed HR of ~0.6914 or less (approximately a 4.46-month or greater improvement over the median OS from 10 months in the standard treatment arm).

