If the expected number of PFS events is not observed by the time the analysis is conducted, the remaining alpha as defined by the spending function will be accelerated to the analysis at that time, and the success boundary for PFS will be recalculated for the actual number of events observed at that time considering the correlation between the interim and final PFS analyses data. Likewise, if the timing of events occurs faster than anticipated, the test boundary at the final PFS analysis will be adjusted to use the remaining Type I error not spent at earlier analysis.

Final Analysis: final OS analyses

The final analysis will take place when:

- 1) At least 222 deaths are observed between one experimental treatment and standard treatment in subjects with PD-L1 CPS 20 (H7 and H11);
- 2) At least 359 deaths are observed between one experimental treatment and standard treatment in subjects with PD-L1 CPS 1 (H8 and H12);
- 3) At least 455 deaths are observed between one experimental treatment and standard treatment in all subjects (H9, H10, H13 and H14);
- 4) All subjects have been followed up for at least 23 months.

The final analysis is expected to occur ~44 months after study start. For any hypothesis listed above, if superiority has not been declared at IA1 or IA2, the specified number of deaths is to be observed for the final analysis. If the expected number of deaths for a hypothesis is not observed by the time that the trial is open for 44 months, the timing of the final analysis may

be delayed for up to 2 months or when the target death event numbers are observed, whichever occurs first. This calendar trigger will enable a suitable follow-up after IA2 and prevent the trial from continuing to an unreasonable duration. If at the time of the final analysis, the number of deaths for one hypothesis is not the same as specified above, the boundary at the final analysis will be adjusted to use the remaining Type I error not spent at earlier analyses.

Table 23 Decision Guidance at Each Analysis

Timing of Analysis	Testing	Expected number of events	Value at boundary	Efficacy Boundary [†]
IA1 (interim PFS analyses and interim OS analyses)				
30 mos. from study start; all 825 subjects enrolled and followed up for at least 9 months	PFS mono/combo vs. SOC in subjects with PD-L1 CPS 20 (H1/H4)	~211	Z statistic p-value (one-sided) Approx. observed HR	3.0329 0.0012 0.6585

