	PFS mono/combo vs. SOC in subjects with PD-L1 CPS 1 (H2/H5)	~337	Z statistic p-value (one-sided) Approx. observed HR	3.0304 0.0012 0.7186
	PFS mono vs. SOC in all subjects (H3)	~423	Z statistic p-value (one-sided) Approx. observed HR	3.0304 0.0012 0.7446
	PFS combo vs. SOC in all subjects (H6)	~423	Z statistic p-value (one-sided) Approx. observed HR	3.6551 0.0001 0.7007
	OS mono/combo vs. SOC in subjects with PD-L1 CPS 20 (H7/H11)	~171	Z statistic p-value (one-sided) Approx. observed HR	2.7808 0.0027 0.6531
	OS mono/combo vs. SOC in subjects with PD-L1 CPS 1 (H8/H12)	~278	Z statistic p-value (one-sided) Approx. observed HR	2.7754 0.0028 0.7948
	OS noninferiority mono/combo vs. SOC in all subjects (H9/H13)*	~352	Z statistic p-value (one-sided) Approx. observed HR	2.7754 0.0028 0.8926
	OS superiority mono/combo vs. SOC in all subjects (H10/H14)	~352	Z statistic p-value (one-sided) Approx. observed HR	2.7754 0.0028 0.7439

Timing of Analysis	Testing	Expected number of events	Value at boundary	Efficacy Boundary [†]
IA2 (interim OS analyses and final PFS analyses)				
38 mos. from study start; all 825 subjects enrolled and followed up for at least 17 months	PFS mono/combo vs. SOC in subjects with PD-L1 CPS 20 (H1/H4)	~237	Z statistic p-value (one-sided) Approx. observed HR	2.9788 0.0014 0.679
	PFS mono/combo vs. SOC in subjects with PD-L1 CPS 1 (H2/H5)	~378	Z statistic p-value (one-sided) Approx. observed HR	2.9792 0.0014 0.7358
	PFS mono vs. SOC in all subjects (H3)	~474	Z statistic p-value (one-sided) Approx. observed HR	2.9792 0.0014 0.7605
	PFS combo vs. SOC in all subjects (H6)	~474	Z statistic p-value (one-sided) Approx. observed HR	3.6331 0.0001 0.7162
	OS mono/combo vs. SOC in subjects with PD-L1 CPS 20 (H7/H11)	~205	Z statistic p-value (one-sided) Approx. observed HR	2.6398 0.0041 0.6914
	OS mono/combo vs. SOC in subjects with PD-L1 CPS 1 (H8/H12)	~332	Z statistic p-value (one-sided) Approx. observed HR	2.6425 0.0041 0.7479
	OS noninferiority mono/combo vs. SOC in all subjects (H9/H13)*	~421	Z statistic p-value (one-sided) Approx. observed HR	2.6425 0.0041 0.9272
	OS superiority mono/combo vs. SOC in all subjects (H10/H14)	~421	Z statistic p-value (one-sided) Approx. observed HR	2.6425 0.0041 0.7727

Timing of Analysis	Testing	Expected number of events	Value at boundary	Efficacy Boundary [†]
Final Analysis (Final OS Analysis)				

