~ 44 mos. from study start	OS mono/combo vs. SOC in subjects with PD-L1 CPS 20 (H7/H11)	≥222	Z statistic p-value (one-sided) Approx. observed HR	2.5644 0.0052 0.7084
	OS mono/combo vs. SOC in subjects with PD-L1 CPS 1 (H8/H12)	≥359	Z statistic p-value (one-sided) Approx. observed HR	2.5641 0.0052 0.7627
	OS noninferiority mono/combo vs. SOC in all subjects (H9/H13)*	≥455	Z statistic p-value (one-sided) Approx. observed HR	2.5641 0.0052 0.9435
	OS superiority mono/combo vs. SOC in all subjects (H10/H14)	≥455	Z statistic p-value (one-sided) Approx. observed HR	2.5641 0.0052 0.7862

[†] Efficacy decision rules for OS presented in table do not account for any alpha shifting from other hypotheses as a result of a successful analysis. P-values based on spending functions determine significance of tests; hazard ratios corresponding to significance are approximate.

*NI bounds are calculated with HR=0.85 under the alternative to establish noninferiority (NI margin=1.2).

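### Table 23's hazard-ratio bound for OS in PD-L1 CPS 1 at interim analysis 1 is misprinted: 0.7948 should be about 0.717

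*Combined protocol and SAP*

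**What the plan says.** Section 8.2.9.2 builds each OS boundary from a spending function: "a Hwang-Shih-DeCani alpha-spending function with gamma parameter (-4) is constructed to implement group-sequential efficacy boundaries". The OS bounds in Table 23 "are based on a nominal overall one-sided alpha level of 0.7% each to pembrolizumab monotherapy vs. standard treatment", with the same level for the combination comparison. For OS in CPS 1 at interim analysis 1 the text expects about "278 deaths between one experimental arm and standard treatment in subjects with PD-L1 CPS 1 (H8 and H12"). The final analysis requires: "At least 359 deaths are observed between one experimental treatment and standard treatment in subjects with PD-L1 CPS 1 (H8 and H12").

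For CPS 1, Table 23 then prints Z, one-sided p and approximate observed hazard ratio at the bound as follows:

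- interim analysis 1: "2.7754 0.0028 0.7948"
- interim analysis 2: "2.6425 0.0041 0.7479"
- final analysis: "2.5641 0.0052 0.7627"

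The narrative for interim analysis 1 states no hazard ratio for OS and refers the reader to Table 23. The footnote to the table says that the p-values decide significance, that the hazard ratios are approximate, and that the OS rules shown do not allow for alpha passed on from other hypotheses.

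**The concern.** The cell is out of line with its neighbours before any formula is applied.

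- **Across analyses.** For CPS 1, the p-value at interim analysis 1 (0.0028) is the strictest of the three looks, and that look has the fewest deaths. Its hazard ratio (0.7948) is nevertheless the most lenient, against 0.7479 and 0.7627 later. A smaller p-value with fewer deaths must need a smaller hazard ratio.
- **Across populations.** The all-subjects superiority row at interim analysis 1 has the same Z (2.7754) and more deaths (352), yet its hazard ratio is stricter (0.7439). At equal Z, more deaths must bring the bound closer to 1.

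Table 23 is the decision guidance for two primary OS hypotheses, and this cell is the only hazard ratio the plan gives for them at interim analysis 1. A reader who uses it would take any result between the true bound and 0.7948 as meeting OS superiority, although the Z and p in the same row say it does not.

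**Working it through.** **Inputs**

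- Deaths at interim analysis 1, CPS 1: D = 278; at the final analysis: 359 (Section 8.2.9.2).
- Boundary Z = 2.7754, one-sided p = 0.0028, hazard ratio 0.7948 (Table 23).
- Overall one-sided alpha 0.7%; Hwang-Shih-DeCani spending with gamma -4 (Section 8.2.9.2).
- Equal allocation within each pairwise comparison, since "Subjects will be randomized 1:1:1 between the 3 arms of the trial" (Section 2.1).

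**1. Are Z and p right?** The information fraction is t = 278/359 = 0.7744. Alpha spent = 0.007 × (1 − e^(4t))/(1 − e^4) = 0.00276. As this is the first look, the bound is the normal quantile for that alpha, Z = 2.775. The printed 2.7754 and 0.0028 are confirmed.

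**2. Does the conversion to a hazard ratio reproduce the table?** With 1:1 allocation, HR = exp(−2Z/√D), multiplied by 1.2 for the noninferiority rows. For OS:

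| Row | D | Z | Printed HR | Recomputed HR |
|---|---|---|---|---|
| IA1, CPS 20 | 171 | 2.7808 | 0.6531 | 0.6536 |
| **IA1, CPS 1** | **278** | **2.7754** | **0.7948** | **0.7168** |
| IA1, all, noninferiority | 352 | 2.7754 | 0.8926 | 0.8927 |
| IA1, all, superiority | 352 | 2.7754 | 0.7439 | 0.7439 |
| IA2, CPS 20 | 205 | 2.6398 | 0.6914 | 0.6916 |
| IA2, CPS 1 | 332 | 2.6425 | 0.7479 | 0.7482 |
| IA2, all, noninferiority | 421 | 2.6425 | 0.9272 | 0.9275 |
| IA2, all, superiority | 421 | 2.6425 | 0.7727 | 0.7729 |
| Final, CPS 20 | 222 | 2.5644 | 0.7084 | 0.7088 |
| Final, CPS 1 | 359 | 2.5641 | 0.7627 | 0.7629 |
| Final, all, noninferiority | 455 | 2.5641 | 0.9435 | 0.9436 |
| Final, all, superiority | 455 | 2.5641 | 0.7862 | 0.7863 |

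The eight PFS rows of Table 23 and the eight rows of Table 24 also agree to within 0.0005. Of 28 cells, only this one fails, by 0.7948 − 0.7168 = 0.078.

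**3. Could another convention give 0.7948?** No variant tried comes close.

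- Freedman's formula gives 0.7146.
- An event share of 0.4 or 1/3 in one arm gives 0.7119 or 0.7025.
- Reading the approximate 278 deaths as anything from 274 to 282 gives 0.715 to 0.719.
- Reaching 0.7948 at Z = 2.7754 would take about 584 deaths, against 359 at the final analysis.
- If the trial's whole 2.5% were passed to this hypothesis, alpha spent would be 0.00276 × 0.025/0.007 = 0.0099, Z about 2.33 and the bound about 0.756. That is still below 0.7948.

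**4. What would an observed 0.7948 mean?** Z = (√278/2) × −ln(0.7948) = 1.915, one-sided p = 0.0278 (0.0283 by Freedman's formula). That is about ten times 0.0028.

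**5. In median survival.** With the plan's 10-month control median and exponential survival, 10/0.7948 = 12.58 months, a gain of 2.6 months. The correct bound gives 10/0.7168 = 13.95 months, a gain of about 4.0 months.

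**6. How likely is a result in the gap?** By normal approximation with standard error 2/√278 = 0.120 on the log scale, the estimate falls between 0.717 and 0.795 with probability about 16% if the true hazard ratio is the design value 0.65. If it is 0.75 (an assumption, for illustration) the probability is about 33%.

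**The case against.** The case on the other side accepts that the number is wrong and argues that it does little harm.

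- The footnote makes the p-value decisive, and Table 20 names the stratified log-rank test for OS superiority. The row therefore has one binding criterion, which is correct, and one illustrative conversion. This stands: followed as written, the plan makes no wrong decision.
- The plan recalculates bounds for the actual deaths and for any alpha passed on, so no printed hazard ratio is meant to be applied unchanged. This also stands, but neither adjustment explains 0.7948, as step 3 shows.
- H8 is tested only after H7 is rejected, and H12 only after H11. The cell matters only once OS in CPS 20 has succeeded. This narrows the circumstances but does not remove them.
- Whether the figure reached the DMC charter cannot be seen from these documents.
- The current text dates from June 2022. The DMC had already reviewed safety data by February 2017, and interim analysis 1 was projected at 30 months from study start, so that look has very probably passed. The value of the correction is then mainly to the record, which the sponsor's policy is to submit with the manuscript.

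The word approximate does not rescue the cell. It fairly covers differences of 0.0005 such as those in the other rows, not 0.078.

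**Conclusion.** The concern holds. The boundary hazard ratio for OS in CPS 1 at interim analysis 1 should be about 0.717; the printed 0.7948 corresponds to a one-sided p of 0.028 rather than 0.0028. The Z, the p-value and the expected deaths in that row are consistent with one another and with the stated spending function, so the error is confined to the hazard ratio. The result rests on equal allocation, about 278 deaths, and the usual large-sample link between the log-rank statistic and the log hazard ratio, which the rest of the table follows. The error does not affect type I error, power, sample size or timing as long as the p-value rule is applied. It is a wrong figure in the stated decision guidance for two primary hypotheses and should be corrected.

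**What to change.** In Table 23, interim analysis 1, OS in CPS 1 (H8/H12), replace 0.7948 with about 0.717. Section 8.2.7 names EAST 6 and gsDesign, so regenerate the cell from the design file to get the fourth decimal with the unrounded event count; the printed inputs give 0.7168. Check the DMC charter and any interim report that quotes this bound, and correct them if they carry 0.7948. If interim analysis 1 has already taken place, confirm on file that the decision on H8 and H12 was made on the p-value. The change is one number, with no operational cost and no effect on the design.

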8.2.6 Multiplicity

The overall type I error rate is strongly controlled at 2.5% (one-sided) with:

- 0.19% allocated to each PFS hypothesis of pembrolizumab monotherapy vs. standard treatment (H1) and pembrolizumab in combination with chemotherapy vs. standard treatment (H4) in subjects with PD-L1 CPS 20;
- 0.02% allocated to PFS hypothesis of pembrolizumab in combination with chemotherapy vs. standard treatment in all subjects (H6);
- 0.7% allocated to each OS hypothesis of pembrolizumab monotherapy vs. standard treatment (H7) and pembrolizumab in combination with chemotherapy vs. standard treatment (H11) in subjects with PD-L1 CPS 20;
- 0.7% allocated to OS noninferiority hypothesis of pembrolizumab in combination with chemotherapy vs. standard treatment in all subjects (H13).

For the PFS hypotheses of pembrolizumab monotherapy vs. standard treatment, a fixed sequential testing will be applied in the order of PFS superiority in subjects with PD-L1 CPS 20 (H1), in subjects with PD-L1 CPS 1 (H2), and in all subjects (H3).

For the PFS hypotheses of pembrolizumab in combination with chemotherapy vs. standard treatment, a fixed sequential testing will be applied in the order of PFS superiority in subjects with PD-L1 CPS 20 (H4) and in subjects with PD-L1 CPS 1 (H5). If H5 is rejected, then the corresponding alpha will be fully shifted to PFS superiority hypothesis for all subjects (H6).

If any of the PFS null hypotheses in all subjects (H3 and H6) is rejected, the corresponding alpha level will be shifted and distributed to the OS hypotheses for the corresponding experimental treatment using the graphical approach of Maurer and Bretz (2013) [57].

For the OS hypotheses of pembrolizumab monotherapy vs. standard treatment, a fixed sequential testing will be applied in the order of OS superiority in subjects with PD-L1 CPS 20 (H7), OS superiority in subjects with PD-L1 CPS 1 (H8), OS noninferiority in all subjects (H9) and OS superiority in all subjects (H10). If H10 is rejected, then the corresponding alpha will be essentially fully reallocated and distributed equally to H11 and H13 if not already significant, with a very small fraction (0.002) reallocated to H1.

[figure not shown]

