For the PFS analysis, in the scenario that events have accumulated faster than expected, event-based analysis will not allow for observing tail behavior that has been important in other trials to fully describe the treatment effect over time. For PFS hypotheses, the Lan and DeMets (1989) [62] calendar time method will be used for alpha spending to generate the group-sequential design. The timing and alpha level of the original plan will be maintained for PFS hypotheses, regardless of the number of events observed. The sample space ordering required for group sequential trials as justified by Maurer and Bretz (2013) [57] will be maintained. This ensures strong control of Type I error. The updated bounds for the PFS hypotheses are given in [Table 24](#). The bounds are based on initial alpha allocation. A Hwang-Shih-DeCani [63] (-1.073) spending function has been used to implement alpha spending for PFS hypotheses for monotherapy versus SOC in all populations (H1, H2, and H3) and combination therapy versus control with PD-L1 CPS1 and CPS20 (H4 and H5). A Hwang-Shih-DeCani (-3.079) spending function has been used for the PFS hypothesis for combination therapy versus control in all subjects (H6). The actual boundaries and the alpha level will be determined from the overall alpha level after any alpha shifting as a result of a successful analysis. The alpha level at the final analysis for the PFS hypotheses (IA2) will be calculated based on alpha reallocation, the alpha used at the interim analysis, and the actual number of events at IA1 and the final PFS analysis (IA2). The bounds given in [Table 24](#) will be adjusted accordingly.

Table 24 Decision Guidance for PFS hypotheses at Each Analysis

Timing of Analysis	Testing	Expected number of events	Value at boundary	Efficacy Boundary [†]
IA1 (interim PFS analyses)				
30 mos. from study start; all 825 subjects enrolled and followed up for at least 9 months	PFS mono/combo vs. SOC in subjects with PD-L1 CPS 20 (H1/H4)	~211	Z statistic p-value (one-sided) Approx. observed HR	3.0357 0.0012 0.6581
	PFS mono/combo vs. SOC in subjects with PD-L1 CPS 1 (H2/H5)	~337	Z statistic p-value (one-sided) Approx. observed HR	3.0357 0.0012 0.7184
	PFS mono vs. SOC in all subjects (H3)	~423	Z statistic p-value (one-sided) Approx. observed HR	3.0357 0.0012 0.7441
	PFS combo vs. SOC in all subjects (H6)	~423	Z statistic p-value (one-sided) Approx. observed HR	3.7190 0.0001 0.6965
IA2 (final PFS analyses)				

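### The spending parameter stated for PFS hypotheses H1 to H5 (-1.073) does not give Table 24's bounds (-1.703 does), and the gamma -4 PFS rule that Table 24 replaces was never withdrawn

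*Combined protocol and SAP*

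**What the plan says.** Two PFS boundary rules appear in the plan.

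**Calendar rule (8.2.9.2, paragraph before Table 24).** PFS uses Lan-DeMets calendar-time spending. For H1 to H3: "A Hwang-Shih-DeCani [63] (-1.073) spending function has been used to implement alpha spending for PFS hypotheses for monotherapy versus SOC in all populations"; the same sentence extends it to H4 and H5. H6 has its own parameter, -3.079. On timing and alpha: "The timing and alpha level of the original plan will be maintained for PFS hypotheses, regardless of the number of events observed". On the bounds: "The updated bounds for the PFS hypotheses are given in" Table 24. For H1/H4 at interim analysis 1 (IA1) Table 24 prints "3.0357 0.0012 0.6581" (Z, one-sided p, hazard ratio), and for H6 "3.7190 0.0001 0.6965". These rest on the initial allocation, and "The actual boundaries and the alpha level will be determined from the overall alpha level after any alpha shifting".

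**Gamma -4 rule.** Sections 8.1.3, 8.2.7 and the opening of 8.2.9.2 assign a Hwang-Shih-DeCani function with gamma -4 to every PFS and OS hypothesis. The IA1 text in 8.2.9.2 adjusts PFS bounds if event counts differ from plan. It and Table 23 still print the resulting PFS cutoffs, including hazard ratio 0.7007 (Z 3.6551) for H6 at IA1.

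Section 8.2.6 allots one-sided 0.19% to each of H1 and H4 and 0.02% to H6, and passes all of H5's alpha to H6 once H5 is rejected.

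**The concern.** A reader who applies the stated -1.073 to the stated analysis times does not get Table 24. Because actual bounds are to follow alpha shifting, bounds may have to be regenerated from a function, so the parameter and the governing rule must be clear.

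The two rules also disagree. One moves the IA1 PFS alpha with the event count; the other fixes it. They give different H6 cutoffs at IA1. The word 'updated' implies replacement, but no sentence withdraws the gamma -4 PFS text. The calendar paragraph also opens with the case of events accruing faster than expected, so it can be misread as conditional. PFS is a dual-primary endpoint, and a result between the two cutoffs would be significant under one rule and not under the other.

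**Working it through.** **Inputs.** Alpha 0.0019 (H1 to H5) and 0.0002 (H6), from 8.2.6. IA1 at 30 months and IA2 at 38 months, from 8.2.9.2, so t = 30/38 = 0.7895. PFS events 211/237 (CPS 20), 337/378 (CPS 1) and 423/474 (all subjects).

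**Formulas.** Alpha spent by t = alpha × (1 − e^(−γt)) / (1 − e^(−γ)). IA1 Z is the upper normal quantile of that alpha. Cutoff hazard ratio = exp(−2Z/√events).

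**Control: H6, stated γ = -3.079.** 0.0002 × 10.368/20.737 = 0.000100, Z = 3.7190. Table 24 prints 3.7190, so the method is right.

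**H1 to H5 at IA1.**

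| γ | Alpha spent | Z |
|---|---|---|
| -1.073 (stated) | 0.0019 × 1.3329/1.9241 = 0.001316 | 3.0077 |
| -1.703 | 0.0019 × 2.8362/4.4904 = 0.001200 | 3.0357 |
| Table 24 | 0.0012 | 3.0357 |

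For H1/H4 at 211 events the cutoff hazard ratio is 0.6609 with Z 3.0077 and 0.6584 with Z 3.0357.

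**Solving for γ.** Spending exactly 0.0012 of 0.0019 at 30/38 needs -1.7033. Spending exactly 0.0001 of 0.0002 needs -3.0787, which rounds to the stated -3.079. One rule, keeping the IA1 alpha as printed to four decimals, explains both parameters if the first is -1.703.

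**Other readings of -1.073 fail.** On event fractions it gives Z 2.951 to 2.952. To give 3.0357 it would need t = 0.7412, or 28.2 of 38 months, a time the plan does not mention.

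**Table 24 controls alpha.** With correlation √(IA1 events/IA2 events), its printed pairs spend 0.001897 (H1/H4), 0.001901 (H2/H5), 0.001899 (H3) and 0.000200 (H6). IA2 bounds solved from the printed IA1 Z, without any γ, are 2.9766, 2.9758 and 2.9752, against 2.9775, 2.9755 and 2.9755 printed.

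**Gamma -4 against the calendar rule at IA1.**

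| Case | Gamma -4, event fraction | Calendar rule |
|---|---|---|
| H1/H4, 211 of 237 events | 0.00121 | 0.00120 |
| H1/H4, assumed 190 to 225 of 237 | 0.00084 to 0.00155 | 0.0012 |
| H6 at 0.02% | 0.000129 (Table 23 HR 0.7007) | 0.000100 (Table 24 HR 0.6965) |
| H6 at 0.02% + 0.19% = 0.21% | 0.00135 (HR 0.7470) | 0.00105 (HR 0.7415) |

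Both tables print p = 0.0001 for H6 at 0.02%, so the difference shows only in Z and the hazard ratio. The last row takes H6's own parameter, -3.079, at the raised alpha.

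**Mixing sources.** A -1.073 IA1 bound with Table 24's IA2 bound spends 0.001972, 0.001976 and 0.001974 of 0.0019 (H1/H4, H2/H5, H3). Table 23's H6 IA1 bound with Table 24's H6 IA2 bound spends 0.000218 of 0.0002.

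**Alpha shifts to H1 and H4.** Taking 0.7% as the alpha released, H1 gains 0.002 × 0.7% and its IA1 cutoff becomes 0.001326 (-1.073) or 0.001209 (-1.703). H4 gains 0.001 × 0.7%: 0.001321 or 0.001204.

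**The case against.** The strongest reply is that little turns on the parameter. Table 24's printed bounds are the decision guidance, and they control alpha. H2, H3 and H5 inherit 0.19% unchanged, and H1 and H4 can gain only tiny fractions. The overspend for H1 to H5 needs an analyst to ignore the printed IA1 bound yet keep the printed IA2 bound, whereas the plan derives IA2 alpha from the alpha actually used at IA1. This stands: the effect for H1 to H5 is narrow. The digit swap is also an inference, and the fault could lie in the machine-read text.

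On the leftover text, the calendar paragraph is specific to PFS and calls its bounds updated. The footnote to Table 23 speaks of OS decision rules and that to Table 24 of PFS rules. A careful reader would follow Table 24. But replacement is only implied, and the event-adjustment sentence directly contradicts the calendar paragraph.

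The plan does not expressly say which parameter spends alpha arriving at H6 from H5. If the 0.19% kept its own spending, the IA1 cutoff would be 0.0012 + 0.0001 = 0.0013, close to the gamma -4 figure. Using H6's own function is the natural reading of the paragraph and of the graphical group-sequential method it cites, but it is an assumption.

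Finally, this is Amendment 13, dated June 2022, and PFS testing was planned at 30 and 38 months from study start, so an erratum may be the only practical route.

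**Conclusion.** Both parts hold. The stated -1.073 does not produce Table 24: it spends 0.001316 at IA1, not 0.0012. A value of -1.703 does, and the H6 check supports that reading. The gamma -4 PFS text remains and conflicts with the calendar rule on event adjustment and on the H6 bound.

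The consequence is small for H1 to H5 at planned event counts. It is larger for H6 after H5 is rejected (0.00105 against 0.00135), given that H6 keeps its own function, and for event counts away from plan. Type I error is controlled if one rule is applied throughout. No stated PFS power needs to change: for H1/H4 it is 89.4% with -1.073 and 89.6% with -1.703, against 90% stated. This should be fixed because the rule for a dual-primary endpoint should be single and reproducible.

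**What to change.** 1. Check -1.073 against the source PDF and then the design output (8.2.7 names EAST 6 and gsDesign). If the source carries it and the output confirms the swap, correct it to -1.703.
2. Add to 8.2.9.2: 'For PFS, the calendar-time spending functions and Table 24 replace the gamma -4 function and the event-based adjustment of the IA1 alpha; actual event counts enter only the IA2 bound.' Also state that H6 keeps its own function when its alpha is raised, if that is intended.
3. Remove the PFS rows from Table 23 and bring the IA1 PFS cutoffs in the 8.2.9.2 text into line with Table 24. With gain = 6/HR − 6 months, these are HR 0.6581 (3.12 months), 0.7184 (2.35), 0.7441 (2.06) and, for H6, 0.6965 (2.61). Confirm the ratios from the design output first: Z 3.0357 gives 0.6584 at 211 events and 0.7444 at 423. The plan labels them approximate.
4. Limit the gamma -4 sentences in 8.1.3, 8.2.7 and 8.2.9.2 to OS.
5. If PFS testing is already done, issue the same text as an erratum and state in the clinical study report which parameter and which table were applied.

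The cost is one checked number, a short added statement and the removal of superseded figures. Design and operations are unaffected.
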